6.1.5 Blinding and Procedures for Unblinding

Neither the participant nor research staff will know what medication condition to which the participant has been assigned. Only the study pharmacists who prepares and mails the participant's medication will know their medication condition assignment. The study physician/APRNs will request a medication order for either Group A or B. They will not know the condition the participant is assigned since the designation of study group is only known by study statistician and pharmacist.

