A novel alert system will be built into the Adverse Event surveys REDCap database such that any severe adverse events (e.g., severe nausea, severe sleep disturbances, severe changes in mood) that are endorsed along with self-report of cessation of pharmacotherapy use will be monitored by research staff, who will consult with the study physician/APRN from the Tobacco Treatment Service/PI [name] when indicated for clinical assessment and management. We believe this alert system will improve varenicline medication adherence if the pharmacist/APRN/physician can quickly follow-up on any side effects that may be associated with pharmacotherapy use and call the patient with any recommended dose adjustments. All dose adjustments will be recorded in our REDCap database.

Guided Self-Change Pamphlet: All groups will receive this pamphlet as a brief behavioral component of the intervention. This 3-page pamphlet includes information on how to reduce and quit e-cigarettes on their own (on Page 1), how to prevent relapse to combustible cigarettes (for mono vapers who quit combustible cigarettes by vaping; on Page 2), and how to enroll in the online This is Quitting services (described above; on Page 3).

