6.1.3 Dosage, Administration, Schedule

Dose and schedule: We are using the same dose of the oral medication for vapers as we would for cigarette smokers. The participants will be given a dose titrated to 2mg daily which aligns with the current FDA approved dose for smoking cessation. The varenicline prescription will follow the standard induction period: varenicline 0.5 mg once per day for Days 1-3, varenicline 0.5 mg twice per day for Days 4-7, then varenicline 1 mg twice per day (when varenicline reaches peak efficacy for tobacco cessation). Participants will remain on varenicline for 8 weeks total. Dose adjustments (e.g., reduction to 0.5 mg twice per day if 1 mg is not well tolerated) will be allowed at the discretion of the clinical pharmacist/APRN/physician. The entire 8-week supply of varenicline will be shipped at week 1 according to the Pharmacy's workflow..

Medication Schedule: Both groups will follow the same medication schedule (listed below).

- Days 1-3: 0.5mg (or matching placebo) study pill once per day
- Days 4-7: 0.5mg (or matching placebo) study pill twice per day
- Weeks 2-8: 1mg or matching placebo) study pill twice per day

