6.2.3 Adverse Events Definition and Reporting

Adverse Events:

Participants will have the phone numbers of the Co-PIs, [name] [contact]) and [name] [contact]) and will be prompted to contact them if an adverse event occurs, along with the previously mentioned adverse event procedures. If a participant contacts the research team due to an adverse event, the event will be appropriately addressed, and the event will be reported per the criteria below. Adverse events will also be tracked via weekly assessments, where they will be able to rate the incident as mild, moderate, or severe. The research staff, with the guidance of [name] (for MUSC) and [name] (for Yale), will track the relatedness of the incident to study medication. The variables that we will encourage the pharmacist/APRN to assess include severe renal impairment, history of serious hypersensitivity or skin reactions to varenicline, an immediate (within 2 weeks) post myocardial infarction period, serious arrhythmias, unstable angina pectoris, or hemodynamically or electrical instability. We will determine if any adverse events result in dropouts or are serious according to FDA guidelines.

Serious adverse events, whether unanticipated or anticipated, will be reported immediately (within 24 hours) to the MUSC or Yale Institutional Review Board. The PIs will evaluate the adverse event and determine whether the adverse event affects the Risk/Benefit ratio of the study and whether modifications to the protocol or the consent procedures are required.

Plans for reviewing and reporting non-serious anticipated or unanticipated adverse events: Any participants' experiences of anticipated and unanticipated adverse events will be reported on an annual basis to the MUSC Institutional Review Board.

Plan for grading adverse events. Serious Adverse Events (SAE). The FDA's definition of serious adverse events (21 CFR 312) will be used. Serious Adverse Events include any untoward medical occurrence that at any dose results in death or the immediate risk of death, hospitalization, or the prolonging of an existing hospitalization, persistent or significant disability/incapacity or a congenital anomaly/birth defect, new cancer, or medication overdose. Adverse events will be defined and graded for risk as follows:

Coding of Severity:

- 0 = No adverse event or within normal limits
- 1 = Mild adverse event
- 2 = Moderate adverse event
- 3 = Severe, resulting in psychiatric or medical hospitalization

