7.11 Study Monitoring

[name], the PI, will be responsible for monitoring the data, assuring protocol compliance, and conducting the safety reviews at the specified frequency that must be conducted at a minimum of every 6 months (including when reapproval of the protocol is sought), which is appropriate for a study deemed to be of minimal risk. [name] will review the frequency of anticipated and unanticipated adverse events overall and by study arm with key personnel. The focus of the evaluation will be to determine whether the study should continue unchanged, require modification/amendment, continue or close to enrollment. [name], the Yale University IRB, and the National Institutes of Health have the authority to stop or suspend the study or require modifications.

[name] will also lead a weekly research meeting with key personnel to review the status of all enrolled participants and discuss the eligibility of potential participants. At this weekly meeting, [name] will review study progress (i.e., recruitment goals, retention, protocol adherence). Any adverse events will be reviewed at this meeting including serious adverse events that may have been attended to outside of this weekly meeting. An annual progress report will be submitted to NIH and the Yale University IRB that lists and summarizes adverse events; documents whether adverse event rates are consistent with pre-study assumptions; summarizes recruitment and retention and reason for dropouts; and

summarizes study progress related to the stated aims.

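### Prescribers who also adjust doses order study drug under one of two group letters, so inferring what one letter means would unblind every participant ordered under that code

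*Combined protocol and SAP*

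**What the plan says.** Section 6.1.5 promises that participants and research staff will not know the assignment. It then sets out how drug is ordered: "The study physician/APRNs will request a medication order for either Group A or B". The safeguard is that "the designation of study group is only known by study statistician and pharmacist". No participant-level or kit-level code is described.

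The people who order by letter also have clinical discretion. Under section 6.1.3 dose adjustments "will be allowed at the discretion of the clinical pharmacist/APRN/physician", and sections 5.1 and 6.3 repeat this. Section 5.1 sends severe adverse events reported together with stopping the drug to research staff, "who will consult with the study physician/APRN from the Tobacco Treatment Service/PI" when indicated. Section 6.2.3 has research staff, under investigator guidance, who "will track the relatedness of the incident to study medication".

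Section 7.11 makes the PI responsible for "conducting the safety reviews at the specified frequency that must be conducted at a minimum of every 6 months". At these reviews the PI "will review the frequency of anticipated and unanticipated adverse events overall and by study arm with key personnel". The PI also leads a weekly meeting with key personnel to "review the status of all enrolled participants" and go over any adverse events.

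**The concern.** A two-letter code hides what a letter means but not who shares it. A prescriber who has ordered for ten participants knows how those ten divide between the arms, and one fact, which letter is active, is all that keeps them blind. With a separate code per participant, a correct guess about one person says nothing about the next.

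Section 7.11 adds a source from which that fact might be inferred, because adverse events are tabulated by arm and varenicline has recognisable side effects (section 2.1.2 lists nausea and unusual dreams among others). Nothing in the protocol says that those who order by letter are kept away from the by-arm review or from what is learned there.

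At stake is the blinding of people who make discretionary decisions: lowering a dose, what is said in calls to participants, judging relatedness, and withdrawing a participant, which section 6.3.7 allows investigators to do at any time. The primary outcome is self-reported abstinence with no biomarker (sections 5.2.1 and 6.2.5), so what staff convey to participants could matter. Section 6.4.1 intends the effect sizes to be used to design a later trial.

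**Working it through.** **How many one decoded letter reveals.** Sections 5.1 and 6.3 give 20 participants per site at two sites: 20 + 20 = 40, which agrees with section 5.3.1. Twenty are to receive varenicline, leaving 40 − 20 = 20 on placebo. With two letters, knowing one gives the other. If the letters mean the same at both sites, one inference covers up to 40 participants; if they differ by site, up to 20. A single prescriber can apply it only to participants whose letter they know. With participant-specific codes it covers 1.

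**How easily the letter could be guessed.** This supposes a by-arm table labelled A and B.

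- Assumed, because the documents give no rates: nausea in 20%, 30% or 40% on varenicline and in 10% or 15% on placebo.
- Arm size n at a review: if 40 are enrolled evenly over about 24 months (study length from the Synopsis, even pace assumed) and the arms stay balanced, each 6-month review adds 40 ÷ 4 = 10 participants, or 5 per arm. So n = 5 at 6 months, 10 at 12 months and 20 once enrolment is complete.
- X ~ Bin(n, varenicline rate) and Y ~ Bin(n, placebo rate), independent. The rule is to call the letter with more nausea active and toss a coin on ties.
- P(right) = P(X > Y) + ½ P(X = Y).

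Two cases in full:

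- n = 5, 20% vs 15%: 0.4093 + 0.3353/2 = 0.577.
- n = 20, 40% vs 10%: 0.9839 + 0.0104/2 = 0.989.

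A guess that is right is not the same as knowing. A stricter measure is the chance that, from a 50:50 start and with the two rates known, the posterior probability of the correct letter exceeds 0.90. Each cell shows P(right), then this confident-and-correct probability.

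| Varenicline vs placebo | n = 5 | n = 10 | n = 20 |
|---|---|---|---|
| 20% vs 10% | 65.9% / 3.6% | 72.9% / 16.6% | 81.1% / 40.7% |
| 30% vs 10% | 77.9% / 33.4% | 87.0% / 61.3% | 94.7% / 84.8% |
| 40% vs 10% | 86.5% / 50.2% | 94.5% / 79.8% | 98.9% / 96.0% |
| 20% vs 15% | 57.7% / 0.0% | 61.2% / 0.0% | 65.9% / 1.1% |
| 30% vs 15% | 70.8% / 8.5% | 78.7% / 29.1% | 87.3% / 57.7% |
| 40% vs 15% | 81.0% / 43.1% | 89.7% / 70.2% | 96.5% / 90.2% |

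**Comparison with participant-specific codes.** Guessing varenicline for anyone with nausea and placebo otherwise is right with probability ½ × varenicline rate + ½ × (1 − placebo rate). This gives 55% to 65% with placebo at 10% (for example ½ × 0.40 + ½ × 0.90 = 0.65) and 52.5% to 62.5% with placebo at 15%. Each such guess concerns one person only.

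**If the table is labelled by treatment instead.** Section 7.11 does not say which labelling is used. Named arms would show the PI and key personnel arm-level safety results directly. Identifying a letter would then need one more step: matching those totals to event counts by letter.

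**The case against.** The strongest reply is that the chain is not complete on paper. The letters are held by the physician/APRNs, while the by-arm review is for the PI and key personnel, and no section says that prescribers belong to that group or see the table. This stands. The overlap is plausible, since sections 5.1 and 6.3 have the physician, nurse practitioners and PI share the medical review, but it is an inference. What the text supports is that nothing separates the two.

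A reader might infer that all 40 assignments fall at once. No section says that the letters are shared across sites. Section 6.1.2 has one drug service encapsulating drug and placebo, which points towards a common code; section 6.1.6 has two pharmacies packaging and labelling. The 40 is therefore an upper figure, and using it needs knowledge of every participant's letter.

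A reader might also infer that the planned adverse event comparison is biased directly. Section 6.4.2 compares only the proportion of participants reporting emergent events. Under section 6.2.3 participants rate severity themselves in weekly assessments, and formal attribution is coded only from grade 3 up. Dose changes and relatedness judgements do not enter that test.

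The primary outcome is also partly protected. It is self-reported, section 6.2.1 has the weekly surveys entered directly into the database by participants, and section 6.4.1 plans a sensitivity analysis that counts missing outcomes as vaping. Finally, 20 per arm is reached only when enrolment is complete and few treatment decisions remain; at the earlier reviews confident decoding is much less frequent. Clinicians can in any case guess individual arms from side effects, although a shared letter carries a guess from one participant to others.

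**Conclusion.** The point holds as a weakness in the blinding procedure that is cheap to remove. The ordering rule tells prescribers which of their participants share an arm. The by-arm safety review could supply the meaning of the letter, and the protocol contains no barrier between the two.

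Under the assumed nausea rates and an A/B-labelled table, the simple guess is right 57.7% to 86.5% of the time with 5 per arm, 61.2% to 94.5% with 10 and 65.9% to 98.9% with 20. Confident and correct decoding occurs in 0% to 50.2%, 0% to 79.8% and 1.1% to 96.0% respectively. These figures rest on one symptom, assumed rates, balanced arms and even enrolment.

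The plausible routes to bias are discretionary dose changes, staff contact, relatedness judgements and investigator withdrawals. The documents show that decoding is possible, not that it happened or will happen, and they give no basis for calculating any bias in abstinence.

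**What to change.** Rewrite section 6.1.5 so that the physician/APRNs order study drug by participant ID only, with the dispensing pharmacist looking up the assignment on the statistician's list. Use the same ID-based order for dose reductions in both arms. No clinical or research staff would then see a group letter.

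Add one sentence stating that a pharmacist who adjusts doses or calls participants is not the dispensing pharmacist. Section 6.1.5 makes the preparing pharmacist unblinded, while sections 5.1 and 6.1.3 let a pharmacist follow up side effects and adjust doses, and nothing says that these are different people.

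The cost is a small change to the order form, the pharmacy workflow and the protocol wording. Sample size, visits and analyses are unaffected. Letters already seen cannot be unlearned, so only participants not yet randomized benefit. Moving the by-arm safety review to someone outside the team is not part of this recommendation: it would need an extra person and would replace the only by-arm safety review that the protocol describes.

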6.1.6 Packaging/Labelling

We will work with the Investigational Drug Service (IDS) pharmacy (MUSC) and Yale-New Haven Pharmacy (Yale) to package and label varenicline. Both packaging and labelling will be done within the IDS pharmacy, following all applicable laws. Under no circumstances will non-credentialed study staff package or label the medication. The IDS pharmacy (MUSC) and Yale-New Haven Pharmacy (YALE) will package and label the varenicline under our prescriber's order. Once a participant is enrolled into the study, the medication, in original packaging, will be mailed or directly delivered distributed to the participant by research staff.

This study is under review for an Investigational New Drug Application exemption.

6.1.7 Storage Conditions

We will use the YNHH Investigational Drug Service to prepare the study medication and store it...

6.1.8 Concomitant therapy

N/a

6.1.9 Restrictions

No restrictions

6.2 Assessments

6.2.1 Efficacy

Study Assessments

The following tools will be used for the assessments conducted at baseline (week 0) and end of follow-up (Week 0, 8 & 12).

Demographics (Week 0): This questionnaire will collect basic demographic information for each subject including gender, ethnicity/race, employment status, etc.

Smoking/Tobacco Use History (Week 0): This will collect basic info about smoking and smoking cessation history, prior varenicline use, e-cigarette history, tobacco and nicotine product flavor preference, etc.

Modified Questionnaire on Smoking Urges (QSU) (Week 0, 8 & 12): This 3-item assessment is used to examine smoking related urges such as desire to smoke, anticipation of immediate positive outcome, etc.³¹E-cigarette Dependence (Week 0 & 8): The NIH Patient-Reported Outcomes Measurement Information System (PROMIS) measure for daily smokers has also been adapted to measure for use of other tobacco products.^{30, 40} This is a 4-item e-cigarette dependence questionnaire that measures withdrawal and craving.

E-cigarette Dependence Index (Week 0 & 8): This is a 10-item e-cigarette dependence questionnaire that measures difficulty quitting, withdrawal and cravings.⁵⁷

Subjective Effects Cigarettes and E-cigarettes (Week 0, Week 4): Participants will report on subjective evaluation about cigarettes and e-cigarettes. Subjective evaluation includes items derived from the Modified E-Cigarette Evaluation Questionnaire (meCEQ)⁵⁸ that have also been adapted for alternate tobacco products. It measures the degree to which participants experience reinforcing effects from smoking and e-cigarettes. The scale yields five clusters or domains: Smoking Satisfaction, Psychological Reward, Aversion, Enjoyment of Respiratory Tract Sensations, and Craving Reduction.⁵⁶

Patient Health Questionnaire-9 (PHQ9) (Week 0 and Bi-Weekly): which assesses for depression and includes an item on suicidal ideation.⁵⁰

Wisconsin Withdrawal Scale Brief (WSWS2-B): This 6-item scale assesses current symptoms of nicotine withdrawal including cravings and irritability.⁵⁹

Weekly Electronic Assessments: Participants will be asked to complete a brief compensated assessment to assess e-cigarette use, use of other tobacco products including cigarettes, and daily medication adherence. These Assessments be completed weekly throughout the entirety of the study. Assessments will assess vaping sessions/puffs per day, use of other tobacco products, medications/products used, purposes of that use (to reduce/quit), next-

day e-cigarette use/other tobacco use/quit intentions, and mood/affect. The assessment will also assess e-cigarette brand, concentration, and habits surrounding e-cigarette use (i.e., location, type of device, and flavor choice). Weekly abstinence will be assessed in three different ways: "Have you quit today?", "Have you used an e-cigarette in the past three days?", and "Have you used an e-cigarette in the past 7 days?" To track medication adherence, the assessment will also ask how many varenicline pills that participant took per day. This will not replace traditional adverse event assessment (below) but complement (and enrich) them. We have established procedures to auto-send an email or SMS text (their choice) on a set schedule. SMS text messaging is possible via Twilio, embedded within our REDCap system, which allows participants to complete a survey directly from their phone, without having to access a webpage. Note that assessments are not completed via texting, just prompted via text with link to REDCap. Participants can choose to receive their assessment invitations via email if they wish, again with a link to a secure REDCap survey. Thus, per eligibility criteria above, we require participants to have smartphone or other device that has internet capacity. Assessments consist of a brief (<2 minutes) survey, directly enter an online protected database (REDCap) through secure encryption; all PHI is protected. Participants will be compensated for compliance based on % assessments completed (described below).

Exit Survey: This survey, designed for the study, will be conducted for all participants. Questions to ascertain participants' reactions to the different intervention conditions (i.e., varenicline, booklet) (e.g., overall satisfaction, perceived helpfulness, etc.), whether they utilized any of the external resources in the booklet (i.e., This is Quitting program) and their reactions, as well as any other use of other medications (e.g., NRT), and behavioral strategies that they used to reduce their e-cigarette use during the study (e.g., titrate e-cigarette nicotine dose, change flavors or switch to unflavored).

6.2.2 Safety and Pregnancy-related policy

Verification of Non-Pregnancy: Females ages ≤ 55 will be mailed a commercially available pregnancy test to verify non-pregnancy. Written confirmation of negative pregnancy test via REDCap will be required prior to enrollment in the trial. Participants are also informed that they should let us know if they become pregnant during the trial. Medications will not be sent until this verification is in place. These procedures are based on the MUSC IRB approved STARS protocol (MUSC IRB Pro00098479).

6.2.3 Adverse Events Definition and Reporting

Adverse Events:

Participants will have the phone numbers of the Co-PIs, [name] [contact]) and [name] [contact]) and will be prompted to contact them if an adverse event occurs, along with the previously mentioned adverse event procedures. If a participant contacts the research team due to an adverse event, the event will be appropriately addressed, and the event will be reported per the criteria below. Adverse events will also be tracked via weekly assessments, where they will be able to rate the incident as mild, moderate, or severe. The research staff, with the guidance of [name] (for MUSC) and [name] (for Yale), will track the relatedness of the incident to study medication. The variables that we will encourage the pharmacist/APRN to assess include severe renal impairment, history of serious hypersensitivity or skin reactions to varenicline, an immediate (within 2 weeks) post myocardial infarction period, serious arrhythmias, unstable angina pectoris, or hemodynamically or electrical instability. We will determine if any adverse events result in dropouts or are serious according to FDA guidelines.

Serious adverse events, whether unanticipated or anticipated, will be reported immediately (within 24 hours) to the MUSC or Yale Institutional Review Board. The PIs will evaluate the adverse event and determine whether the adverse event affects the Risk/Benefit ratio of the study and whether modifications to the protocol or the consent procedures are required.

Plans for reviewing and reporting non-serious anticipated or unanticipated adverse events: Any participants' experiences of anticipated and unanticipated adverse events will be reported on an annual basis to the MUSC Institutional Review Board.

Plan for grading adverse events. Serious Adverse Events (SAE). The FDA's definition of serious adverse events (21 CFR 312) will be used. Serious Adverse Events include any untoward medical occurrence that at any dose results in death or the immediate risk of death, hospitalization, or the prolonging of an existing hospitalization, persistent or significant disability/incapacity or a congenital anomaly/birth defect, new cancer, or medication overdose. Adverse events will be defined and graded for risk as follows:

Coding of Severity:

- 0 = No adverse event or within normal limits
- 1 = Mild adverse event
- 2 = Moderate adverse event
- 3 = Severe, resulting in psychiatric or medical hospitalization
- 4 = Life-threatening adverse event
- 5 = Fatal adverse event

Coding of Attribution will be made for adverse events grade 3 and above (i.e., serious adverse events):

- 1 = Unrelated to study interventions
- 2 = Unlikely relationship to study interventions
- 3 = Possible relationship to study interventions
- 4 = Probable relationship to study interventions
- 5 = Definite relationship to study intervention

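### Section 6.2.3 merges severity with seriousness: a severe event without hospitalisation has no grade, and grade 3 and above is not the same set as the serious adverse events

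*Combined protocol and SAP*

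**What the plan says.** Section 6.2.3 sets out three linked items.

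- **SAE definition.** It follows the FDA definition and covers death or immediate risk of death, and new or prolonged hospitalisation. It then adds "persistent or significant disability/incapacity or a congenital anomaly/birth defect, new cancer, or medication overdose".
- **Severity code, 0 to 5.** Grade 0 is no adverse event, 1 mild, 2 moderate, 4 life-threatening and 5 fatal. Grade 3 is "3 = Severe, resulting in psychiatric or medical hospitalization".
- **Attribution rule.** "Coding of Attribution will be made for adverse events grade 3 and above (i.e., serious adverse events"), on a five-point scale from unrelated to definite.

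The same section also says "Adverse events will also be tracked via weekly assessments, where they will be able to rate the incident as mild, moderate, or severe". Research staff, guided by a named lead at each site, "will track the relatedness of the incident to study medication"; no grade limit is attached. It adds: "We will determine if any adverse events result in dropouts or are serious according to FDA guidelines".

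Section 5.1 describes an alert for "any severe adverse events (e.g., severe nausea, severe sleep disturbances, severe changes in mood") when the participant also reports stopping the medication. Hospitalisation is not part of that description.

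Section 6.4.2 plans one safety comparison: the proportion of participants in each group who report an adverse event.

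**The concern.** Severity is how intense an event is. Seriousness is whether it meets a regulatory outcome criterion. Section 6.2.3 writes a seriousness criterion, hospitalisation, into the definition of one severity grade, and then uses grade to stand for seriousness when it decides which events get an attribution code.

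Two things follow. A severe event handled at home has no natural place on the scale, so its grade depends on who codes it, and the grade decides whether it receives an attribution code. And an SAE that does not reach grade 3 may or may not be coded for attribution, depending on which half of the rule staff follow. At stake is how consistent the severity and attribution record is across two sites. Section 6.4.1 says the results will be used to design a larger trial, and the safety record would be a natural input to that.

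**Working it through.** The plan states no figure on this point and no arithmetic applies. The check sets the definitions in Section 6.2.3 side by side.

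**Step 1: does every event of grade 3 or above count as an SAE?** Grade 3 as written requires hospitalisation, grade 4 is life-threatening and grade 5 is fatal. Each meets a criterion in the SAE definition. So yes, on the literal text.

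**Step 2: does every SAE reach grade 3?**

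| SAE criterion | Matching grade |
|---|---|
| Death | 5 |
| Immediate risk of death | 4 |
| Hospitalisation | 3 |
| Prolonged hospitalisation | 3, on a loose reading |
| Disability or incapacity | none stated |
| Birth defect | none stated |
| New cancer | none stated |
| Medication overdose | none stated |

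An event under one of the last four criteria, without hospitalisation or threat to life, is an SAE by definition but does not satisfy grade 3. So grade 3 and above is a proper subset of the SAEs, and the equivalence in the attribution rule fails in that direction. For such an event the grade limit says not to code attribution, while the parenthesis says to code it.

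**Step 3: where does a severe event without hospitalisation go?** It is more than moderate, so it exceeds grade 2. It does not meet the hospitalisation condition, so it is not grade 3. It is neither life-threatening nor fatal. No grade fits. The protocol expects such events: the alert in Section 5.1 names severe nausea, sleep disturbance and mood change, and the weekly assessment lets participants rate an event as severe. Neither asks about admission.

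**Step 4: what happens under each way out?**

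- Coded as grade 2, the event is recorded as moderate and gets no attribution code.
- Coded as grade 3, it gets an attribution code but falls in a category that the section labels serious, although it need not meet any SAE criterion. The equivalence then fails in the other direction as well.

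**Step 5: is the attribution limit consistent with the rest of the section?** Relatedness is to be tracked for adverse events generally, with no grade limit, while the 1-to-5 attribution code is limited to grade 3 and above. The section does not say how relatedness is recorded below that limit, so the two statements need reconciling.

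**Step 6: what depends on grade or attribution?** SAEs are identified by the FDA definition and go to the institutional review board within 24 hours, with no reference to grade. The comparison in Section 6.4.2 uses any adverse event. Nothing in Section 6.4 uses grade or attribution.

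**The case against.** The strongest reply is that little turns on this. SAE identification and reporting do not depend on grade, relatedness is tracked anyway, and no planned test uses either code. Section 7.11 also provides a weekly meeting at which any adverse events are reviewed, so divergent coding between sites could be noticed. All of that stands, and it is why the point is minor. The meeting does not close the gap, though, because the protocol gives it no rule for grading a severe event without admission.

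It can also be said that the scale is an ordinal risk scale, so such an event simply defaults to grade 2, and that the participant's rating and the Section 5.1 alert are separate tools with their own thresholds. Different thresholds are not in themselves a contradiction. But the text states no default, and grade 2 is labelled moderate, so the default would record an event the protocol calls severe as something less.

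Some stronger readings are tempting and should not be drawn.

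- A reader might infer that SAEs could go unreported. Reporting follows the SAE definition, not the grade.
- A reader might note that, under Section 6.2.1, "the assessment will also ask how many varenicline pills that participant took per day", and infer that excess intake without symptoms would be an SAE at grade 0 or 1. Grade 0 means no adverse event, the SAE definition presupposes a harmful medical event, and overdose is not defined, so the documents do not support that example.
- A reader might infer that a hospitalised but non-severe event falls below grade 3. That assumes a pure severity scale. The protocol's own scale names hospitalisation in grade 3, and such an event can reasonably be placed there.
- A reader might take the number of unlinked SAE criteria in the table as a measure of impact. They are items in a list, not expected events, and birth defect and new cancer are remote possibilities in a 12-week study.

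**Conclusion.** The point holds on the text. The severity scale has no place for a severe event without hospitalisation, and the attribution rule equates two sets that its own section defines differently. It is a minor defect. It affects how consistently severity and attribution are recorded; SAE reporting, the planned safety comparison and the primary outcome are unaffected.

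The conclusion rests on reading hospitalisation as part of the definition of grade 3 rather than as an illustration, and on there being no further coding instruction beyond the protocol. The documents give no adverse event rates, so the number of events affected cannot be estimated. Severe outpatient events are the likelier case in practice, since nausea and sleep problems are among the side effects listed in Section 2.1.2. Confidence in the textual finding is high.

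**What to change.** Amend Section 6.2.3 in four places:

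1. Define grade 3 by severity alone, without the hospitalisation condition, and leave the other grades as they are.
2. Record seriousness in a separate yes/no field, using the section's own SAE definition.
3. Apply the attribution code to every SAE whatever its grade, and to every severe event whether or not it is serious. Remove the parenthesis that equates grade with seriousness; once grade 3 means severity only, it would be wrong in both directions.
4. Reconcile the attribution rule with the general tracking of relatedness: say whether lower-grade, non-serious events use the same five-point scale.

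The cost is a text edit, one extra field in the database and a little clinician time for the additional attribution codes. No visit, test or sample-size figure changes.
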